**Pharmacokinetic Statistical Analyses**

that fit the data well.

- Scatter plots of natural log-transformed saliva gepotidacin concentrations versus the natural log-transformed plasma gepotidacin concentrations will be plotted and a regression line will be fitted.
- Scatter plots of natural log-transformed saliva gepotidacin PK parameters versus the natural log-transformed plasma gepotidacin PK parameters will also be performed for the AUC(0- $\infty$ ), AUC(0-t), and Cmax.

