4.3. Type and Number of Subjects

In Part 1, up to 16 subjects with normal renal function will be matched to approximately 8 subjects with moderate renal impairment, and approximately 8 subjects with severe renal impairment and/or subjects with ESRD not on hemodialysis for a total of approximately 32 subjects. In Part 2 (optional), approximately 4 to 8 subjects with normal renal function (if enrolled), approximately 4 to 8 subjects with mild renal impairment, and approximately 4 to 8 subjects with ESRD on hemodialysis will be enrolled for a total of approximately 12 to 24 subjects.

If there are a sufficient number of subjects with normal renal function enrolled in Part 1 (Group A) that match subjects with renal impairment in other groups, a determination will be made regarding enrollment of matching subjects with normal renal function in Part 2 (Group D). In addition, if subjects prematurely discontinue the study, additional replacement subjects may be enrolled at the discretion of the Sponsor in consultation with the investigator.

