9.4.3. Other Analyses

9.4.3.1. Exploratory Analyses

Saliva (subjects in Part 1 only):

AUC(0-∞)	Area under the concentration-time curve from time 0 (predose) extrapolated to infinite time
AUC(0-t)	Area under the concentration-time curve from time 0 (predose) to time of last quantifiable concentration
CL	Systemic clearance
C _{max}	Maximum observed concentration
λ _z	Terminal-phase rate constant
t _{1/2}	Terminal phase half life
T _{max}	Time to first occurrence of C _{max}
V _z	Volume of distribution of the terminal phase

Saliva concentrations (subjects in Part 1 only; as data permit) of gepotidacin and the associated PK parameters will be listed, and summary statistics (n, mean, median, SD, minimum, maximum, and CV) will be presented by day and treatment. Mean and individual saliva concentration versus time profiles will be presented graphically on linear and semilogarithmic scales.

An exploratory analysis will be performed to explore the relationship between saliva and plasma concentrations. Natural log-transformed saliva gepotidacin concentrations versus the natural log-transformed plasma gepotidacin concentrations will be plotted and a regression line will be fitted. A similar analysis will also be performed for the AUC(0-∞), AUC(0-t), and C_{max}.

Detailed descriptions of the analyses in this study will be presented in the RAP.

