**Table 7 Derived Saliva Pharmacokinetic Parameters (subjects in Part 1 only)**

Parameter	Parameter Description
AUC(0-t)	Area under the concentration-time curve from time 0 (predose) to time of last quantifiable concentration, to be calculated using the linear trapezoidal rule for each incremental trapezoid and the log trapezoidal rule for each decremental trapezoid.
AUC(0-∞)	Area under the concentration-time curve from time 0 (predose) extrapolated to infinite time, calculated as: $AUC = AUC(0-t) + C(t) / \lambda z$
%AUCex	The percentage of AUC (0-∞) obtained by extrapolation (%AUCex) will be calculated as: $[AUC(0-inf) - AUC(0-t)] / AUC(0-inf) \times 100$
Cmax	Maximum observed concentration, determined directly from the concentration-time data.
Tmax	Time to first occurrence of Cmax
t1/2	Terminal phase half-life will be calculated as: $t_{1/2} = \ln 2 / \lambda z$
λz	Terminal-phase rate constant
CL	Systemic clearance, calculated as: $CL = \text{Dose} / AUC(0-inf)$
Vss	Volume of distribution at steady-state of parent drug, calculated as: $V_{ss} = MRT(0-inf) * (CL)$
Vz	Volume of distribution of the terminal phase, calculated as: $V_z = \text{Dose} / (AUC(0-inf) * \lambda z)$
RAUC(0-t)	The ratio of the AUC(0-t) observed in saliva relative to the AUC(0-t) in plasma, calculated as: $RAUC(0-t) = AUC(0-t) \text{ saliva} / AUC(0-t) \text{ plasma}$
RAUC(0-∞)	The ratio of the AUC(0-∞) observed in saliva relative to the AUC(0-∞) in plasma, calculated as: $RAUC(0-\infty) = AUC(0-\infty) \text{ saliva} / AUC(0-\infty) \text{ plasma}$

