### 7.1.3.2. Statistical Analysis of Pharmacokinetic Parameters

The following pharmacokinetic statistical analyses will only be performed, if sufficient data is available (i.e. if subjects have well defined plasma profiles).

Pharmacokinetic Statistical Analyses
Endpoint(s)

 
Plasma primary pharmacokinetic (PK) endpoints include AUC(0-∞), AUC(0-t) and Cmax of gepotidacin, as data permit
 

Model Specification

 
The log-transformed AUC(0-∞), AUC(0-t), and Cmax values for gepotidacin in the renal impairment groups and normal renal function groups will be compared using an analysis of variance.
 
Linear regression analysis will be used to evaluate the relationships between estimated renal function and relevant PK parameters (e.g., AUC, Cmax, and CL).
 
An exploratory analysis will be performed to explore the relationship between saliva and plasma concentrations and PK parameters.
 

Model Checking & Diagnostics

 
Refer to Appendix 9: Model Checking and Diagnostics for Statistical Analyses.
 

Model Results Presentation

 
Statistical analysis by ANOVA will be presented in tabular format with geometric mean ratios between renal impairment groups and normal renal function groups, and 90% CIs for the ratios of AUC(0-∞) and Cmax for gepotidacin. Example SAS Code:   <pre>PROC MIXED; CLASS GRPID; MODEL LOGPKPARAM = GPRID/DDFM=KR; LSMEANS GRPID; ESTIMATE 'B VS A' GPRID -1 1 0/CL ALPHA=0.1; ESTIMATE 'C VS A' GPRID -1 0 1/CL ALPHA=0.1;RUN;</pre> 
 
Statistical analysis by linear regression will be presented in tabular format if the data permits with identification of linear functions that fit the data well, the resulting slopes will provide a comparison of any difference in the response of the gepotidacin IV treatment as renal function changes. Example SAS Code:   <pre>PROC MIXED; MODEL LOGPKPARAM = RENAL_FUNCTION/S DDFM=KR; ODS OUTPUT SOLUTIONF=S; RUN;</pre> 
 
Statistical analysis by linear regression will be presented in graphical format with scatter plots of PK parameters by eGFR and PK parameters by Clcr with identification of linear functions
 

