
visit days on the analyses and interpretation of the results will be assessed as appropriate.
 
 
Reporting for Data Listings:                             
 
Planned and actual time relative to study drug dosing will be shown in listings (Refer to IDSL Statistical Principle 5.05.1).
 
Unscheduled or unplanned readings will be presented within the subject's listings.
 
Visits outside the protocol defined time-windows (i.e. recorded as protocol deviations) will be included in listings but omitted from figures, summaries and statistical analyses.
 
 
 
	
Unscheduled Visits	

 
Unscheduled visits will not be included in summary tables.
 
Unscheduled visits will not be included in figures.
 
All unscheduled visits will be included in listings.
 
	
Descriptive Summary Statistics	
Continuous Data	Refer to IDSL Statistical Principle 6.06.1
Categorical Data	N, n, frequency, %
Reporting of Pharmacokinetic Concentration Data	
Descriptive Summary Statistics	Refer to IDSL Statistical Principle 6.06.1 Assign zero to NQ values (Refer to GUI_51487 for further details)
Reporting of Pharmacokinetic Parameters	
Descriptive Summary Statistics (Log Transformed)	
N, n, geometric mean, 95% CI of geometric mean, standard deviation (SD) of logged data and [between and or within] geometric coefficient of variation (CVb/w (%)) will be reported.
 $CV_b (\%) = \sqrt{(\exp(SD^2) - 1) * 100}$ 
(SD = SD of log transformed data)

Parameters Not Being Log Transformed	T max , %AUC ex , lambda z , lambda z_lower , lambda z_upper , lambda z_no. of points , t last
Summary Tables	lambda z_lower , lambda z_upper , lambda z_no. of points , t last

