9.11.6. Pharmacokinetic Tables

Pharmacokinetic : Tables					
No.	Population	IDSL / TST ID / Example Shell	Title	Programming Notes	Deliverable [Priority]
PK Concentration Data					
3.1	PK	PK01	Summary of Gepotidacin Plasma Pharmacokinetic Concentration-Time Data (units) by Group	Blood samples for PK analysis will be collected at 1 predose time point and 0.25, 0.5, 1.0, 1.5, 2.0, 2.5, 3.0, 4.0, 6.0, 8.0, 12.0, 24 ,36 and 48 hours after dosing. If mean is below the level of quantification, report the mean value as NQ.	SAC [1]
3.2	PK	PK01	Summary of Gepotidacin Urine Concentrations (units)	Urine collection intervals for subjects with normal renal function (Group A and Group D) include 0 (pre-dose), 0 to 2 hours, 2 to 4 hours, 4 to 6 hours, 6 to 8 hours, 8 to 12 hours, 12 to 24 hours, 24 to 36 hours, and 36 to 48 hours. Urine collection intervals for subjects with renal impairment (Group B, Group C, and Group E) include 0 hour (pre-dose), 0 to 6 hours, 6 to 12 hours, 12 to 24 hours, 24 to 36, and 36 to 48 hours. If mean is below the level of quantification, report the mean value as NQ.	SAC[1]

Pharmacokinetic : Tables					
No.	Population	IDSL / TST ID / Example Shell	Title	Programming Notes	Deliverable [Priority]
3.3	PK	PK01	Summary of Gepotidacin Saliva Concentrations (units) by Renal Function	Blood samples for PK analysis will be collected at 1 predose time point and 0.25, 0.5, 1.0, 1.5, 2.0, 2.5, 3.0, 4.0, 6.0, 8.0, 12.0, 24 ,36 and 48 hours after dosing.If mean is below the level of quantification, report the mean value as NQ. Part 1 subjects only.	SAC [1]
3.4	PK	PK01	Summary of Gepotidacin Dialysate Concentrations (units)	Blood samples for PK analysis will be collected at 1 predose time point and 0.25, 0.5, 1.0, 1.5, 2.0, 2.5, 3.0, 4.0, 6.0, 8.0, 12.0, 24 ,36 and 48 hours after dosing. If mean is below the level of quantification, report the mean value as NQ. Part 2 subjects only. Part 2 subjects in Group F only	SAC[1]
3.5	PK	PK01	Summary of Gepotidacin Dialyzer Plasma Concentration (units)	Blood samples for PK analysis will be collected at 1 predose time point and 0.25, 0.5, 1.0, 1.5, 2.0, 2.5, 3.0, 4.0, 6.0, 8.0, 12.0, 24 ,36 and 48 hours after dosing. If mean is below the level of quantification, report the mean value as NQ. Part 2 subjects in Group F only	SAC[1]

Pharmacokinetic : Tables					
No.	Population	IDSL / TST ID / Example Shell	Title	Programming Notes	Deliverable [Priority]
PK Parameters Tables					

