## 9.11.7. Pharmacokinetic Figures

Pharmacokinetic : Figures					
No.	Population	IDSL / TST ID / Example Shell	Title	Programming Notes	Deliverable [Priority]
Concentration Plots					
3.1	PK	PKCF4	Mean Gepotidacin Plasma Concentrations by Renal Function (Linear and Semi-Log)	Dashed line represents the LLQ. Present all treatment groups in the same plots.	SAC [1]
3.2	PK	PKCF4	Mean Gepotidacin Urine Concentrations by Renal Function (Linear and Semi-Log)	Dashed line represents the LLQ. Present all treatment groups in the same plots. Plot concentration at the collection midpoint.	SAC [1]
3.3	PK	PKCF4	Mean Gepotidacin Saliva Concentrations by Renal Function (Linear and Semi-Log)	Dashed line represents the LLQ. Present all treatment groups in the same plots.	SAC [1]
3.4	PK	PKCF1P	Individual Gepotidacin Plasma Concentrations by Renal Function (Linear and Semi-Log)	Dashed line represents the LLQ. Present all treatment groups in the same plots.	SAC [1]
3.5	PK	PKCF1P	Individual Gepotidacin Urine Concentrations by Renal Function (Linear and Semi-Log)	Dashed line represents the LLQ. Present all treatment groups in the same plots. Plot concentration at the collection midpoint.	SAC [1]
3.6	PK	PKCF1P	Individual Gepotidacin Saliva Concentrations by Renal Function (Linear and Semi-Log)	Dashed line represents the LLQ. Present all treatment groups in the same plots.	SAC [1]

Pharmacokinetic : Figures					
No.	Population	IDSL / TST ID / Example Shell	Title	Programming Notes	Deliverable [Priority]
Parameter Plots					
3.6	PK Parameters	PK_F1	Scatter Plot to Explore the Relationship between Gepotidacin Plasma Pharmacokinetic Parameters by Renal Function	Present all treatment groups in the same plots. Repeat for CrCL. Repeat for parameter AUC(0-t) and CL	SAC [1]
3.7	PK Parameters	PK_F2	Scatter Plot to Explore the Relationship between Gepotidacin Urine Pharmacokinetic Parameters by Renal Function	Present all treatment groups in the same plots. Repeat for CrCL.	SAC [1]
3.8	PK Parameters	PK_F3	Scatter Plot to Explore the Relationship between Gepotidacin Saliva Pharmacokinetic Parameters by Renal Function	Present all treatment groups in the same plots. Repeat for CrCL. Repeat for parameter AUC(0-t) and CL	SAC [1]
Exploratory Objectives					
3.9	PK	PK_F4	Scatter Plot of Gepotidacin Saliva and Plasma Concentrations by Renal Function	Present all treatment groups in the same plots.	SAC [1]

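### SAP Table 7 reports IV dose divided by saliva AUC as systemic clearance, with volumes built on it; drop these saliva parameters and say what the saliva–plasma line is for

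*SAP*

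**What the plan says.** **Saliva parameters.** The title of SAP Table 7 begins "Derived Saliva Pharmacokinetic Parameters (subjects in Part 1 only". The table defines CL, under the description systemic clearance, as Dose/AUC(0-∞); Vss as MRT(0-∞) × CL; and Vz as Dose/(AUC(0-∞) × λz). It also defines RAUC(0-t) and RAUC(0-∞), the saliva/plasma ratios of AUC. Saliva CL, Vss and Vz go into Table 3.8 and Listing 48. Saliva CL is also named in the programming notes for Figure 3.8 (saliva parameters against renal function) and Figure 3.10 (saliva against plasma parameters).

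**Saliva Vss.** The Analysis text of the protocol synopsis restricts Vss to plasma, and the saliva list in Protocol 9.4.3.1 omits it. The endpoint tables in the synopsis and in Protocol Section 3 include it for saliva, as do SAP 2.2 and Table 7. SAP 2.1 declares no change from the protocol's analysis.

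**Saliva against plasma.** SAP 7.1.3.2 states that "An exploratory analysis will be performed to explore the relationship between saliva and plasma concentrations and PK parameters". Log saliva and log plasma "concentrations will be plotted and a regression line will be fitted". The listed output is Figure 3.9, "Scatter Plot of Gepotidacin Saliva and Plasma Concentrations by Renal Function". The same section asks for log–log parameter plots for AUC(0-∞), AUC(0-t) and Cmax; the note to Figure 3.10 names both AUCs and CL, but not Cmax.

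**The concern.** Dose/AUC is a systemic clearance when the AUC is measured in plasma, through which the whole IV dose passes. Saliva is a fluid sampled alongside plasma, and the dose does not pass through it. Dividing the full dose by saliva AUC mixes true clearance with how far drug partitions into saliva, and the two volumes inherit the problem.

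The label matters because the study asks how clearance changes with renal function. Figure 3.8 would show a quantity called clearance falling or rising with eGFR, and Table 3.8 would put its values in the same report as plasma CL.

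The concentration plot is a lesser matter. Each subject contributes many pairs to one line, and the plan gives no subject term, no covariance structure and no statement that the line is only descriptive.

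**Working it through.** The documents give no precision or sample-size figure for the saliva analyses, so there is none to reproduce.

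**1. What saliva CL equals.** Inputs: the formulas in SAP Table 7, and the plasma IV clearance of 43 L/hr in Protocol Appendix 11. Protocol Table 1 agrees with that clearance: 750/17.5 = 42.9 L/hr, using AUC(0-t).

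RAUC = AUC_saliva / AUC_plasma, so

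CL_saliva = Dose / AUC_saliva = Dose / (RAUC × AUC_plasma) = CL_plasma / RAUC.

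The documents give no value of RAUC, so a range is assumed:

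| Assumed RAUC | Saliva CL (L/hr) |
|---|---|
| 0.25 | 43/0.25 = 172 |
| 0.5 | 43/0.5 = 86 |
| 1 | 43/1 = 43 |
| 2 | 43/2 = 21.5 |

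By the same algebra, saliva Vss is plasma Vss × (MRT_saliva/MRT_plasma)/RAUC, and saliva Vz is plasma Vz × (λz_plasma/λz_saliva)/RAUC.

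**2. Comparison between renal groups.** From Protocol Table 1, CL is 42.9 L/hr in normal function and 750/28.9 = 26.0 in severe impairment, a ratio of 17.5/28.9 = 0.61. With RAUC 0.5 in both groups the saliva CL ratio is also 0.61. If RAUC were 0.5 in normal and 1 in severe (assumed), saliva CL would be 85.7 and 26.0, a ratio of 0.30. The level is wrong unless RAUC is 1; the between-group ratio is wrong only if RAUC differs between groups.

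**3. The CL panel of Figure 3.10.** log CL = log Dose − log AUC(0-∞) for either fluid. All Part 1 subjects are planned to receive 750 mg, so the log–log CL plot is the AUC(0-∞) plot with both axes reversed and shifted. Its slope is identical and it adds nothing.

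**4. Pairs available for the concentration line.** Samples are "collected at 1 predose time point and 0.25, 0.5, 1.0, 1.5, 2.0, 2.5, 3.0, 4.0, 6.0, 8.0, 12.0, 24 ,36 and 48 hours", and Protocol Table 3 has the same times for saliva: 1 + 14 = 15 per subject. Part 1 is planned "for a total of approximately 32 subjects". That is 32 × 15 = 480 scheduled pairs. A predose value should be non-quantifiable and has no logarithm, which leaves at most 32 × 14 = 448. SAP 9.3.3 says "Assign zero to NQ values" for concentration summaries, but does not say what happens before taking logs.

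**5. What repeated pairs do to a pooled line.** This was simulated (1,500 runs, 32 subjects × 14 pairs, true slope 1, residual SD 0.5 on the log scale). Plasma profiles were illustrative two-compartment curves with CL 43, 29 and 26 L/hr by group. All variance components are assumptions, since the documents give none.

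| Subject SD: intercept, slope | Mean slope | Actual SD / reported SE of slope | Coverage of naive 95% CI: slope, intercept |
|---|---|---|---|
| 0, 0 | 1.00 | 0.0097/0.0097 = 1.00 | 96%, 94% |
| 0.3, 0 | 1.00 | 0.0107/0.0113 = 0.95 | 96%, 65% |
| 0.5, 0 | 1.00 | 0.0124/0.0137 = 0.91 | 97%, 53% |
| 0.5, 0.1 | 1.00 | 0.0229/0.0145 = 1.58 | 79%, 56% |
| 0.5, 0.2 | 1.00 | 0.0414/0.0167 = 2.48 | 56%, 61% |

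The line itself is not biased. An interval around it could be badly wrong, by an amount that depends on how much slopes vary between subjects.

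**The case against.** The strongest reply is that none of this touches a conclusion. Saliva is exploratory and confined to Part 1; RAUC, which answers the exposure question, is already planned; and saliva CL and Vz are endpoints that the protocol itself lists, so the SAP follows the protocol in deriving them. All of that stands. It limits the importance of the point but does not make the label right.

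Four stronger readings are tempting, and the documents do not support them.

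- *The pooled line is invalid because it treats samples as independent.* The plan states no model, so independence is inferred from silence. SAP Table 3 marks no statistical analysis for concentrations, Figure 3.9 is the only output listed for the line, and no SE, CI or p-value is specified. SAP Appendix 9 allows adjustments based on the data. A descriptive line is not invalidated by clustering.
- *Pooling overstates how well saliva tracks plasma.* The simulated slope averaged 1.00 throughout. In a separate run (32 subjects × 12 pairs, assumed intercept SD 0.4, slope SD 0.15, residual SD 0.2, 5-hour half-life) the pooled R² was about 0.8, against about 0.96 within subject. There, pooling understates tracking.
- *Standard errors are too small by a fixed factor.* The ratio ran from 0.91 to 2.48 across the assumptions above, and with intercept variation alone the slope SE was not understated.
- *The protocol excludes saliva Vss.* It says so in one place and lists saliva Vss as an endpoint in two others. This is a contradiction, not a rule.

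The absence of Cmax from the note to Figure 3.10 may also be harmless: the note lists repeats, and the base display could be Cmax. The text does not say.

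**Conclusion.** The point holds for saliva CL, Vss and Vz. SAP Table 7 gives an explicit formula whose result is not what its label says. The error in CL is a factor of 1/RAUC: fourfold too high at an assumed ratio of 0.25, twofold too low at 2, and nil only at 1. The algebra needs no assumption; the illustrated sizes rest on the protocol's 43 L/hr and the assumed ratios. The saliva Vss entries conflict within the protocol and must be reconciled.

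For the concentration line, the finding is only that its purpose and model are unstated. That becomes a statistical problem if an SE, CI or p-value is added. The whole point is a minor improvement to exploratory reporting.

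**What to change.** 1. Remove saliva CL, Vss and Vz from SAP Table 7, Table 3.8 and Listing 48, and saliva CL from Figures 3.8 and 3.10. Make the matching edits to the saliva endpoints in SAP 2.2 and the saliva listing entry in SAP 9.3.3. Keep AUC(0-t), AUC(0-∞), Cmax, Tmax, t1/2 with its λz, and both RAUC ratios.
2. Name Cmax in Figure 3.10, as SAP 7.1.3.2 requires.
3. Bring the protocol's four saliva lists into agreement (synopsis endpoint table, synopsis Analysis text, Section 3 and 9.4.3.1), and record the change in SAP 2.1.
4. For Figure 3.9, either state that the line is descriptive and will carry no SE, CI or p-value, or, if inference is wanted, specify a model of log saliva on log plasma with a random intercept and slope per subject. State how predose and non-quantifiable values are handled before logging.

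**Cost.** No new data and fewer displays. The one real cost is a documented change to exploratory endpoints that the protocol lists. Nothing is lost on clearance, because Dose/saliva AUC can be recovered from the reported AUC. The mixed model would need its own specification, since the SAP names no procedure for the saliva line; the descriptive option needs one sentence.

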## 7.2. Safety Analyses

### 7.2.1. Overview of Planned Analyses

The safety analyses will be based on the Safety population, unless otherwise specified.

Table 8 provides an overview of the planned analyses, with further details of data displays being presented in Appendix 11: List of Data Displays.

**Table 8 Overview of Planned Safety Analyses**

Display Type	Absolute				Change from Baseline			
	Summary		Individual		Summary		Individual	
	T	F	F	L	T	F	F	L
Exposure								
Extent of Exposure				Y				
Adverse Events								
All AEs	Y			Y				
All Drug-Related AEs	Y			Y				
Serious AEs				Y				
Withdrawal AEs				Y				
Laboratory Values								
Clinical Chemistry	Y			Y	Y			
Hematology	Y			Y	Y			
Urinalysis (Dipstick)	Y			Y				
ECGs								
ECG Findings	Y			Y				
ECG Values	Y			Y	Y			
Vital Signs								
Vital Signs	Y			Y	Y			
Liver								
Liver Events [1]				Y				
Cardiovascular								
Cardiovascular [1]				Y				
Clostridium Difficile								
Clostridium difficile Testing [1]				Y				
Infusion Site Reactions								
Infusion Site Reaction Events [1]				Y				
Rash Events								
Rash Events [1]				Y				

**NOTES :**

1. Conditional displays, they will only be produced when an event has occurred.
  - T = Table, F = Figure, L = Listing, Y = Yes display generated.
  - Summary = Represents TFL related to any summaries (i.e. descriptive statistics) of the observed raw data.
  - Individual = Represents TFL related to any displays of individual subject observed raw data.

## 9. APPENDICES

Section	Appendix
RAP Section 5 : General Considerations for Data Analyses & Data Handling Conventions	
Section 9.1	Appendix 1 : Time and Events
Section 9.2	Appendix 2 : Treatment States & Phases
Section 9.3	Appendix 3 : Data Display Standards & Handling Conventions 
 
• Study Treatment & Sub-group Display Descriptors
 
• Baseline Definitions & Derivations
 
• Reporting Process & Standards
 

Section 9.4	Appendix 4 : Derived and Transformed Data 
 
• General, Study Population & Safety
 
• Efficacy
 
• Pharmacokinetic
 
• Pharmacodynamic and or Biomarkers
 

Section 9.5	Appendix 5 : Premature Withdrawals & Handling of Missing Data 
 
• Premature Withdrawals
 
• Handling of Missing Data
 

Section 9.6	Appendix 6 : Values of Potential Clinical Importance
Section 9.7	Appendix 7 : Division of Microbiology and Infectious Disease Adult Toxicity Tables for Adverse Event Assessment
Section 9.8	Appendix 8 : Multiple Comparisons and Multiplicity
Section 9.9	Appendix 9 : Model Checking and Diagnostics for Statistical Analyses
Other RAP Appendices	
Section 9.10	Appendix 10 : Abbreviations & Trade Marks
Section 9.11	Appendix 11 : List of Data Displays

